Days Relative to Dosing on Day 1 ^b	-28 to -3	Day -2 to Day 1	2	8	15	22	29	36	43	50	Day 55 to Day 56	57	58	63 - 70 84 - 91	
FSH (females only)	x														
HIV, HepBsAg, HepBcAb, HCVAb, syphilis	x														
Pregnancy test (females only)	x		x	x	x	x	x	x	x	x		x	x		
PF-06882961 PK ⁱ		x		x		x		x	x	x		x	x		
CCI															c
Urine Sampling for:															
Urine drug test	x														
Urinalysis (and microscopy, as appropriate)	x			x		x		x	x	x		x	x		
On-site urine pregnancy test (females only) ^j			x	x	x	x	x	x	x	x		x	x		

- a. Contact may occur via telephone and must occur 28 to 35 days from administration of the final dose of study intervention.
- b. Allowable time window for V3-V10 is ± 1 .
- c. Review glucometer and glucose log only.
- d. Physical examination may be performed at non-specified visits if there are findings during the previous exam or new/open AEs, if appropriate and at investigator discretion.
- C** f. Includes blood pressure and pulse rate; vital signs at Follow up, and early termination visit (if appropriate) are single; Triplicate vital signs should be conducted at Screening, prior to AM dose at 0H and at approximately 4H after AM dose on Days 8, 15, 22, 29, 36, 43, and 50. On Day 57, triplicate vital signs collected at 0H only. When a meal or snack is scheduled at the same time as vital signs, vital signs must be obtained prior to the meal/snack (See [Appendix 9](#)).
- g. 12-lead ECG at Screening, Days 15 and 43, Follow up, and early termination visit (if appropriate) are single; Triplicate ECGs should be conducted prior to AM dose at 0H and at approximately 4H after AM dose on Day 29. On Day 57, triplicate ECGs collected at 0H only. When a meal or snack is scheduled at the same time as an ECG, the ECG must be performed prior to the meal/snack (See [Appendix 9](#)).
- h. During inpatient stays, both AM and PM dosing will occur on the study site, except discharge day (Day 2). On outpatient visit and discharge day, AM dosing will occur at the study site, if applicable.
- i. PK samples to be collected prior to AM dose and at 4H after AM dose on Days 15, 29, and 43. Day 2 sample to be collected at 24H after AM dose on Day 1. Day 50 sample to be collected at 24H after AM dose on Day 49. Day 57 sample to be collected at 24H and 36H after AM dose on Day 56. Day 58 sample to be collected at 48H after AM dose on Day 56.

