6.5.1. Medications for Glycemic Control

The use of other medications for glycemic control is not permitted in this study (see [Appendix 8](#)).

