8.3.1. Time Period and Frequency for Collecting AE and SAE Information

The time period for actively eliciting and collecting AEs and SAEs (“active collection period”) for each participant begins from the time the participant provides informed consent, which is obtained before the participant’s participation in the study (ie, before undergoing any study-related procedure and/or receiving study intervention), through and including a minimum of 28 calendar days, except as indicated below, after the last administration of the study intervention.

Follow-up by the investigator continues throughout and after the active collection period and until the AE or SAE or its sequelae resolve or stabilize at a level acceptable to the investigator and Pfizer concurs with that assessment.

For participants who are screen failures, the active collection period ends when screen failure status is determined.

If the participant withdraws from the study and also withdraws consent for the collection of future information, the active collection period ends when consent is withdrawn.

If a participant definitively discontinues or temporarily discontinues study intervention because of an AE or SAE, the AE or SAE must be recorded on the CRF and the SAE reported using the CT SAE Report Form.

Investigators are not obligated to actively seek AE or SAE after the participant has concluded study participation. However, if the investigator learns of any SAE, including a death, at any time after a participant has completed the study, and he/she considers the event to be reasonably related to the study intervention, the investigator must promptly report the SAE to Pfizer using the CT SAE Report Form.

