10.8. Appendix 8: Prohibited Prior/Concomitant Medications

The following medications are prohibited until the first follow-up visit (ie, Visit 11, Week 9-10), unless stated otherwise. If a participant receives a prohibited medication, the investigator should contact the Sponsor Clinician or Sponsor Medical Monitor to determine if the participant may remain in the study.

Drug Classes and/or Drugs	Timeframe of Restriction Prior to Screening Visit
Thiazolidinediones such as pioglitazone.	90 days
Subcutaneously administered agents for glycemic control (eg, insulin, exenatide, liraglutide, dulaglutide). Note: Short-term (ie, ≤ 7 days) of insulin administration is permitted if participant is hospitalized.	90 days
Pharmacological agents with approved indication for weight loss such as mazindol.	90 days
Oral anti-diabetic medications, including: Biguanides such as metformin, buformin. Sulfonylureas such as acetohexamide, chlorpropamide, glyclopypamide, glibenclamide, gliclazide, glimepiride. Meglitinide analogues such as repaglinide, nateglinide, mitiglinide. DPP-4i such as sitagliptin, alogliptin, saxagliptin, linagliptin, vildagliptin, teneligliptin, anagliptin, trelagliptin, omrigliptin. α glucosidase inhibitors such as acarbose, voglibose, miglitol. SGLT2 inhibitors such as ipragliflozin, luseogliflozin, tofogliflozin, canagliflozin, empagliflozin, dapagliflozin. Anti-hyperglycemic medications, including bromocriptine.	60 days
Systemic glucocorticoids such as prednisone, dexamethasone, triamcinolone, budesonide. Note: As an exception, steroid-containing inhalers, nasal sprays and topical formulations are permitted. Note: Intercurrent treatment with systemic corticosteroids during participation in the study may be permitted if treatment does/will not exceed 7 days.	60 days
Immunosuppressants such as cyclosporine and tacrolimus.	60 days
Appetite or weight modifying medications, including nonprescription or herbals.	60 days
Anti-psychotic medications such as olanzapine, risperidone.	60 days
Coumarin type anticoagulants or other anticoagulants (eg, dabigatran).	60 days
Anticonvulsants if prescribed for seizure disorder.	60 days
Antiarrhythmic medications whose primary mechanism of action is sodium or potassium channel blockade (eg, procainamide, quinidine, propafenone; as well as amiodarone, sotalol).	60 days

Drug Classes and/or Drugs	Timeframe of Restriction Prior to Screening Visit

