3. ENDPOINTS AND BASELINE VARIABLES: DEFINITIONS AND CONVENTIONS

3.1. Primary Endpoint(s)

Incidence of treatment emergent AEs (AEs and SAEs), clinical laboratory abnormalities, vital signs and ECG parameters during the entire study.

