3.1.1. Adverse Events

An adverse event is considered treatment emergent (TEAE) relative to a given treatment if:

- The event starts during the effective duration of treatment (i.e. starting after the first dose but before the last dose plus lag time)

The effective duration of treatment is determined by the lag time. Any event occurring within the lag time, whether this occurs during a break in treatment or at the end of treatment, is attributed to the corresponding treatment period. The lag time is defined by the Pfizer Standard of 365 days post last dose of study intervention.

A 3-tier approach will not be used to summarize TEAEs due to small sample size.

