6.1.1.2. Time to First Occurrence of AEs of Interest

Exploratory summaries on the time to the first occurrence of AEs of interest will be produced using Kaplan-Meier (KM) Curves as described in Section [5.2.3](#). Participants who discontinue from the study, discontinue from IP or initiate glycemic rescue medication prior to the start of the AE event of interest will be censored at the discontinuation/initiation date.

The three AEs of interest are: diarrhea, nausea and vomiting (based on preferred term). A separate KM plot for each AE will be produced separately.

Listings of AEs of interest will be produced.

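### The all-causality TEAE and hypoglycemia tables pool on-treatment events with 28 to 35 days of almost drug-free follow-up, part of it after other glucose-lowering drugs cease to be prohibited; an on-treatment table should be added

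*SAP*

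**What the plan says.** **Window.** The primary endpoint in SAP 3.1 is "Incidence of treatment emergent AEs (AEs and SAEs), clinical laboratory abnormalities, vital signs and ECG parameters during the entire study". SAP 3.1.1 counts events that start after the first dose and before the last dose plus a lag: "The lag time is defined by the Pfizer Standard of 365 days post last dose of study intervention". Events inside the lag are assigned to that treatment, with no exception for other drugs.

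**Collection.** Protocol 8.3.1 has AEs actively collected from consent "through and including a minimum of 28 calendar days, except as indicated below, after the last administration of the study intervention". The final contact, V12, "must occur 28 to 35 days from administration of the final dose of study intervention" (protocol 1.3). Protocol 4.1 places V11 at Day 63-70 and V12 at Day 84-91.

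**Other glucose-lowering drugs.** Protocol 6.5.1 states: "The use of other medications for glycemic control is not permitted in this study", and points to Appendix 8. Appendix 8 sets an end date: "The following medications are prohibited until the first follow-up visit (ie, Visit 11, Week 9-10), unless stated otherwise". Its list includes insulin, injectable GLP-1R agonists, metformin and sulfonylureas. Under protocol 8.2.5.3, a participant discontinued for confirmed hyperglycemia is recommended glycemic treatment, which may fall before V11.

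**Tables.** SAP 6.1.1 plans TEAE incidence and severity tables by arm, all-causality and treatment-related. SAP 6.1.1.1 summarizes hypoglycemic events by arm. Neither states a split by phase or a rule for new drugs. Only the exploratory Kaplan-Meier curves for diarrhea, nausea and vomiting have one (SAP 6.1.1.2): participants who leave the study, stop study drug or "initiate glycemic rescue medication prior to the start of the AE event of interest will be censored at the discontinuation/initiation date".

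**The concern.** A TEAE table is read as a description of what happened on each dose. Here it mixes time on drug with about a month off drug, and in part of that month a participant may be taking a different antidiabetic agent. The events that such an agent could cause are the ones this study watches most closely. The protocol's risk table lists gastrointestinal reactions as a GLP-1R agonist class risk and says that insulin and sulfonylureas raise the risk of hypoglycemia. An event of this kind after V11 would appear under the randomized arm in the all-causality and hypoglycemia tables, with nothing in the table to separate it.

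The tables also differ from the exploratory curves. A first episode of nausea after the start of glycemic rescue is censored in the curve but counted in the incidence table. With about 9 participants per arm and no inferential analysis, the tables and listings carry the whole safety comparison.

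**Working it through.** **Inputs.** Last dose taken as Day 56 (dosing is completed at V10, protocol 4.1). V11 at Day 63-70 and V12 at Day 84-91 (protocol 4.1). Half-life 4.681 to 8.090 h (protocol 2.2.2.2). Lag 365 days (SAP 3.1.1). About 9 participants per arm (protocol 9.2).

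**1. Reproduce the plan's V12 window.** 56 + 28 = Day 84 and 56 + 35 = Day 91, which matches.

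**2. Does the lag exclude any collected event?** 56 + 365 = Day 421. This is 421 - 91 = 330 to 421 - 84 = 337 days after V12, so no event collected up to V12 is excluded. The figure of 365 has no effect of its own; what matters is that no shorter cut-off is used in any TEAE table.

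**3. Time on drug after the last dose.**
- Five half-lives: 5 x 4.681 = 23.4 h; 5 x 8.090 = 40.5 h.
- Fraction left at 48 h, 2^(-48/t½): 0.08% to 1.6%.
- Fraction left at 7 days with the longer half-life, 2^(-168/8.090): below 0.0001%.

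**4. Follow-up counted as treatment-emergent.** 84 - 56 = 28 days (28/84 = 33%) to 91 - 56 = 35 days (35/91 = 38%). If the first 2 days are allowed for washout, the drug-free part is 26/84 = 31% to 33/91 = 36%.

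**5. Part in which Appendix 8 no longer prohibits other glucose-lowering drugs.** Shortest: 84 - 70 = 14 days (14/84 = 17%). Longest: 91 - 63 = 28 days (28/91 = 31%).

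**6. Weight of one participant.** 1/9 = 11.1 percentage points in the incidence of a preferred term, provided that the participant had no earlier event of that term. For common terms this will often fail: nausea was reported at 49.0% in the earlier multiple-dose study (protocol 2.2.2.1).

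**7. Illustration on assumed values; the documents give none.** If k of 9 participants in an arm start another drug, and each has probability q of a new event of a given term, the expected added incidence is k x q / 9. For k = 1, q = 0.10 this is 1.1 points; for k = 5, q = 0.50 it is 27.8 points. For k = 0 it is zero.

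**8. Effect of a 7-day cut-off.** The on-treatment window closes at 56 + 7 = Day 63, the earliest V11. Then 84 - 63 = 21 days (25%) to 91 - 63 = 28 days (31%) move to the follow-up column, including the whole period in step 5.

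**The case against.** The strongest reply is that the window is deliberate. Both documents define the primary endpoint over the entire study, and a lag that reaches past V12 carries this out. That stands: the whole-study table should remain.

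There are also real safeguards. The treatment-related tables rest on causality judged by site staff who are blinded to treatment and must weigh concomitant therapy and timing (protocol 6.3.2 and 10.3.3). Diarrhea, nausea and vomiting get by-week summaries and listings, and hypoglycemic events are listed separately. Concomitant treatments are recorded with start dates (protocol 6.5) and summarized (SAP 6.5.3). In a study of about 36 participants, a careful reader could date each event by hand. This mitigates the problem but does not remove it. The all-causality table is unprotected. The by-week denominators are tied to treatment discontinuation, and the SAP does not say whether follow-up weeks are shown. Table layouts follow sponsor reporting standards that are not in the documents, so a phase split there cannot be ruled out; it is not in the SAP.

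Protocol 6.5.1, read alone, bars these drugs throughout the study. But it refers to Appendix 8, which ends the prohibition at V11, so the two do not settle the matter.

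A reader might infer that the SAP has already recognized drugs started after V11, because the Kaplan-Meier rule mentions rescue. The text does not go that far: it names glycemic rescue medication and does not mention drugs that become allowed later.

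**Conclusion.** The point holds as an inexpensive improvement in reporting. It does not show the endpoint or the lag to be wrong. All collected events to V12 are pooled under the arm, 28 to 35 days of that window follow the last dose, and for 14 to 28 days (17 to 31%) other glucose-lowering drugs are no longer prohibited. No rule in the all-causality or hypoglycemia tables identifies events that follow such a drug.

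Three stronger readings are tempting but not supported:
- *That events caused by new antidiabetic drugs will enter the primary endpoint.* Entry at HbA1c 7 to 10.5% without antidiabetic medication makes starting one plausible, but no passage says that anyone would, or how many.
- *That placebo participants would start sooner, raising placebo rates and shrinking the contrast.* This is conjecture. All arms are off study drug after Day 56, and the documents give no rates by arm, so the direction is unknown.
- *That 33 to 38% of the window is exposed to new drugs.* That share is all follow-up, including the time before V11 when the prohibition still applies to completers.

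The conclusion assumes that the half-life from the earlier study, in participants taking metformin, carries over to Japanese participants without background therapy. The earlier route, through discontinuation for hyperglycemia, matters only if AEs are still collected afterwards. Protocol 7.1 says that such participants do not remain in the study, while 8.3.1 continues collection for at least 28 days after the last dose; these passages need to be reconciled.

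**What to change.** 1. Keep the whole-study TEAE table, as the endpoint is worded.
2. In SAP 6.1.1 and 6.1.1.1, add an on-treatment table from first dose to last dose plus a fixed short lag, for example 7 days (the earliest V11), ending sooner if another glucose-lowering drug is started. Show later events to V12 in a follow-up column.
3. In the AE and hypoglycemia listings, flag any TEAE that starts after another glucose-lowering drug.
4. Reconcile protocol 6.5.1 with the Appendix 8 end date, so that the status of these drugs between V11 and V12 is unambiguous.

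The cost is SAP wording and one more table for each of the two summaries. The dates needed (last dose, AE onset, start of concomitant treatment) are already collected. The downside is that a late drug effect would appear in the follow-up column, but it is still reported there and in the whole-study table.

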3.1.1.1. Hypoglycemia Monitoring

Hypoglycemia AEs will be recorded in the Case Report Form (CRF) as a separate page. Details of when these will be recorded are given in the protocol Section 8.2.5.2.

For programming purposes, the hypoglycemic AE categories are based on the following:

- Severe Hypoglycemia: Severe is checked in the severity criteria of the CRF. This assessment will be made by the principal investigator based on the protocol definition.
- Documented Symptomatic Hypoglycemia: If (2 – Did the subject have symptoms of hypoglycemia?) Yes and (3 – Was blood glucose measured?) Yes and result <70 mg/dL (3.9 mmol/L) on the CRF, but hypoglycemia is not classified as severe.
- Asymptomatic Hypoglycemia: If (2) No and (3) Yes and result <70 mg/dL (3.9 mmol/L) on the CRF, but hypoglycemia is not classified as severe.
- Probable Symptomatic Hypoglycemia: If (2) Yes and (3) No and (3a – If blood glucose was not measured, did symptoms resolve when treated with carbohydrate or glucagon?) Yes on the CRF, but hypoglycemia is not classified as severe.

3.1.2. Electrocardiograms

Standard 12-lead ECG (including heart rate, PR, QT, QTcF intervals and QRS complex) will be obtained at times detailed in the schedule of activities given in the protocol. The average of the triplicate readings collected at each appropriate assessment time will be calculated for each ECG parameter, if applicable.

Change from time-matched baseline for heart rate, PR, QT, QTcF intervals and QRS complex will be calculated for each post baseline measurement.

Baseline is defined as the time-matched value from the average of the triplicate recordings on Day -1.

In addition, the time-matched double difference in heart rate, QT, QTcF, PR and QRS measures is calculated in the following steps: (1) subtract predose value on Day 1 from all postdose values; (2) subtract the value at 0 hours on Day -1 from all other values on Day -1; (3) take the difference between the adjusted postdose value in (1) and its time-matched value in (2).

3.1.3. Vital Signs

Vital sign measurements (blood pressure and pulse rate) will be taken as detailed in the schedule of activities given in the protocol. The average of the triplicate measurements at each appropriate assessment time will be calculated for each blood pressure and pulse rate, if applicable.

Changes from time-matched baseline for supine systolic and diastolic blood pressure and pulse rate will be calculated for each post baseline measurement.

Baseline is defined as the time-matched value from the average of the triplicate recordings on Day -1.

In addition, the time-matched double difference in supine blood pressures and pulse rate measurements is calculated in the following steps: (1) subtract predose value on Day 1 from all postdose values; (2) subtract the value at 0 hours on Day -1 from all other values on Day -1; (3) take the difference between the adjusted postdose value in (1) and its time-matched value in (2).

3.1.4. Laboratory Data

Safety laboratory tests (hematology, chemistry, urine testing and other clinical laboratory tests) will be performed as described in the protocol (Table 2) .

To determine if there are any clinically significant laboratory abnormalities, the safety tests will be assessed against the criteria specified in the sponsor reporting standards. The assessment will take into account whether each participant's baseline test result is within or outside the laboratory reference range for the particular laboratory parameter.

Baseline for all laboratory measurements will be defined as the Day -1, 0H time point for each measure.

Table 2. Protocol-Required Safety Laboratory Assessments

Hematology	Chemistry	Urinalysis	Other
Hemoglobin	BUN	pH	Lipid panel:
Hematocrit	Creatinine	Glucose (qual)	● Total cholesterol
RBC count	eGFR	Protein (qual)	● Direct LDL-C
MCV	Plasma glucose	Blood (qual)	● HDL-C
MCH	Calcium	Ketones	● Triglycerides
MCHC	Sodium	Nitrites	TSH
Platelet count	Potassium	Leukocyte esterase	Free T4
WBC count	Chloride	Urobilinogen	Calcitonin
Total neutrophils (Abs)	AST	Urine bilirubin	Amylase
Eosinophils (Abs)	ALT	Microscopy ^a	Lipase
Monocytes (Abs)	Total bilirubin	Urine pregnancy test	Serum total bile acids
Basophils (Abs)	GGT		PT/INR/aPTT
Lymphocytes (Abs)	Alkaline phosphatase		Serum pregnancy test (β -hCG)
	Uric acid		
	Albumin		At screening and/or Day-2 only:
	Total protein		
 ● FSH^b ● Urine drug screening^c ● Hepatitis B surface antigen ● Hepatitis B core antibody ● Hepatitis C antibody ● Human immunodeficiency virus ● Syphilis
	Additional Tests (Needed for Hy's Law)		
	AST, ALT (repeat) Total bilirubin (repeat) Albumin (repeat) Alkaline phosphatase (repeat) Direct bilirubin Indirect bilirubin Creatine kinase GGT (repeat) PT/INR (repeat) Total bile acids Acetaminophen drug and/or protein adduct levels		

- a. Only if urine dipstick is positive for blood, protein, nitrites, or leukocyte esterase.
- b. For confirmation of postmenopausal status only.
- c. The minimum requirement for drug screening includes cocaine, tetrahydrocannabinol, opiates/opioids, benzodiazepines, and amphetamines (others are site and study specific).

3.2. Secondary Endpoint(s)

3.2.1. Pharmacokinetic Endpoints as Secondary Endpoint

Blood samples for PK analysis of PF-06882961 will be taken according to the schedule of activities given in the protocol.

PK parameters for plasma PF-06882961 following single and multiple dose administration of PF-06882961 will be derived using standard noncompartmental methods, as data permit for each treatment and Day [Day 1 and Day 56], from the concentration time profiles in the table as follows:

Table 3. Pharmacokinetic Endpoints as Secondary Endpoint

Parameter	Definition	Method of Determination	Analysis
Plasma Parameters			
C_{\max}	Maximum plasma concentration observed from time zero to 24 hours	Observed directly from data	ln, D
$C_{\max 1}$	$C_{\max 1}$: maximum plasma concentration during the dosing interval $\tau_1=0$ to 10 hours	Observed directly from data	ln, D
$C_{\max 2}$	$C_{\max 2}$: maximum plasma concentration during the dosing interval $\tau_2=10$ to 24 hours	Observed directly from data	ln, D
T_{\max}	Time for C_{\max}	Observed directly from data as time of first occurrence	R, D
$T_{\max 1}$	Time for $C_{\max 1}$	Observed directly from data as time of first occurrence	R, D
$T_{\max 2}$	Time for $C_{\max 2}$	Observed directly from data as time of first occurrence	R, D
AUC_{24}	Area under the plasma concentration-time profile from time zero to time 24 hours	$AUC_{\tau_1} + AUC_{\tau_2}$	ln, D
$t_{1/2}^*$	Terminal half-life	Log _e (2)/ k_{el} , where k_{el} is the terminal phase rate constant calculated by a linear regression of the log-linear concentration-time curve. Only those data points judged to describe the terminal log-linear decline will be used in the regression.	R, D

Key: D=displayed with descriptive statistics, ln=natural-log transformed, R=raw (untransformed), *=not calculated at Day 1.

CCI

CCI

CCI

CCI

CCI

